		
9) Schedule of activities – addition of allowable window for study visits.
 
10) Section 1.1 Indication - Indication has been added.
 
11) Section 1 - Updated non-clinical and clinical summary information.
 
12) Section 1.2.3: Non-Clinical Experience - update of Clinical experience to reflect most current IB.
 
13) Section 1.2.4: Clinical Experience - update of Clinical experience to reflect most current IB.
 
14) Section 2.2: Endpoints - section added.
 
15) Section 3: Study design – abbreviated.
 
16) Section 4.1: Inclusion Criteria – Inclusion of evidence of a signed informed consent document added.
 
17) Section 4.2: Exclusion Criteria - Added exclusion: Pregnant females; breastfeeding females; females of childbearing potential.
 
18) Section 4.3.1: Contraception – added section to increase clarity.
 
19) Section 5.3 Drug Storage and Accountability - Updated storage conditions for investigational product.
 
20) Section 6: Study Procedures
 
• Addition of possibility for alternative options for study visits added.• Sections 6.1, 6.2 added to increase clarity of required assessments and procedures to be performed at each telephone and clinic visit.
--	--	--

		
21) Section 8: Adverse Event Reporting: Transfer of pharmacovigilance from ICON to Pfizer, Inc. Updated to include Pfizer requirements.
 
22) Section 9.6 Interim Analysis: Addition of interim analysis.
 
23) Sections 10, 11, 12, 13, 14, 15 – replace sections 11 and 12 from FoldRx protocol to reflect Pfizer requirements.

Original protocol	19 June 2009	N/A

This amendment incorporates all revisions to date, including amendments made at the request of country Health Authorities, IRB/ERB, etc.

PROTOCOL SUMMARY

Indication:

Tafamidis is being developed for the treatment of transthyretin amyloidosis, specifically targeting TTR polyneuropathy and cardiomyopathy

Study Objectives:

- To obtain additional, long-term, open-label safety and efficacy data for tafamidis in patients with transthyretin amyloid cardiomyopathy (TTR-CM).
- To continue to provide the investigational product tafamidis to patients with TTR-CM who completed Protocol Fx1B-201.

Study Population:

Male and female patients with V122I or wild-type TTR-CM who have not undergone liver or heart transplantation and who completed Protocol Fx1B-201 (a Phase 2, open-label study to evaluate TTR stabilization, as well as the safety and tolerability of tafamidis). Up to 35 patients are anticipated.

Test Product, Dose, and Mode of Administration:

Tafamidis 20 mg soft gelatin capsule once daily (at the same time each day).

Duration of Treatment: Up to 10 years or until subject has access to tafamidis for TTR-CM via prescription. Upon regulatory approval for the treatment of TTR-CM in their respective country and access to prescription tafamidis, subjects may be withdrawn from the study. Such subjects are considered study completers. The decision to withdraw subjects to transition to commercial supply will be done in consultation between the investigator and the sponsor.

Clinical Endpoints:

Safety

- Incidence of treatment-emergent adverse events;
- Physical examinations;
- Use of concomitant medications;
- Electrocardiograms (ECGs);
- Clinical safety laboratory tests;
- Vital signs.

Efficacy

- Patient Global Assessment;
- New York Heart Association (NYHA) Classification;
- 6-Minute walk test;
- Kansas City Cardiomyopathy Questionnaire (KCCQ);

- Echocardiography;
- Troponin I, troponin T, and amino-terminal B-type natriuretic peptide (NT-pro-BNP);
- Mortality and hospitalization (all cause and cardiac-related).

Inclusion Criteria:

- Evidence of a personally signed and dated informed consent document indicating that the subject (or a legal representative) has been informed of all pertinent aspects of the study.
- Patient successfully completed Protocol Fx1B-201.
- If female, patient is post-menopausal. If male, female partner is post-menopausal; or if female partner is of childbearing potential, then the patient is willing to use an acceptable method of birth control for the duration of the study and for at least three months after the last dose of study medication.
- Patient is, in the opinion of the Investigator, willing and able to comply with the investigational product regimen and all other study requirements.

Exclusion Criteria:

- Patient did not successfully complete Protocol Fx1B-201.
- Chronic use of non-protocol approved non-steroidal anti-inflammatory drugs (NSAIDs), defined as greater than 3 to 4 times/month. The following NSAIDs are allowed: acetylsalicylic acid, etodolac, ibuprofen, indomethacin, ketoprofen, nabumetone, naproxen, nimesulide, piroxicam, and sulindac.
- Patient has a clinically significant medical condition that, in the opinion of the Investigator, would place the patient at an increased risk to participate in the study.
- Pregnant females; breastfeeding females; females of childbearing potential.
- Patient has received a liver or heart transplant.

Study Design:

This is a Phase 3, open-label study designed to obtain additional long-term safety and efficacy data in patients who successfully completed Protocol Fx1B-201. These patients will be treated, with once daily 20 mg oral tafamidis (soft gelatin capsule) for up to 10 years from the date of enrollment in Protocol Fx1B-303, or until subject has access to tafamidis for TTR-CM via prescription. Upon regulatory approval for the treatment of TTR-CM in their respective country and access to prescription tafamidis, subjects may be withdrawn from the study. The decision to withdraw subjects to transition to commercial supply will be done in consultation between the investigator and the sponsor.

Subjects who successfully complete Fx1B-201 will report to the clinical unit on Day 0 to sign the informed consent form and determine eligibility for Protocol Fx1B-303. In addition, on Day 0, subjects will have their entrance criteria reviewed, and medical

histories and demographic characteristics obtained. The physical examination (including weight and vital signs) and the relevant end of study clinical laboratory tests (alkaline phosphatase, alanine aminotransferase, aspartate aminotransferase, blood urea nitrogen, gamma glutamyl transferase, creatinine, total bilirubin, international normalized ratio, troponin I, troponin T, and amino-terminal B-type natriuretic peptide) from Protocol Fx1B-201 will be used for Protocol Fx1B-303. If more than 30 days has elapsed between the final study visit of Protocol Fx1B-201 and Day 0 of Protocol Fx1B-303, an abbreviated physical examination (including weight and vital signs) and clinical laboratory assessments must be performed on Day 0.

Eligible subjects will begin once-daily dosing with 20 mg tafamidis at home on Day 1 (i.e., first dose) and will return to the clinical unit for study visits every 6 months.

Adverse events (AEs) and concomitant medication use will be collected at each 6-month visit to the clinical unit. Blood draws for clinical safety laboratory tests and abbreviated physical examinations (including weight and vital signs) will also be performed at each 6-month clinic visit. ECGs will be performed every 12 months on an annual basis. A telephone call will be made at 3-month intervals between clinic visits to assess safety and use of concomitant medications.

For the evaluation of efficacy, the Patient Global Assessment, NYHA classification, KCCQ, 6-minute walk test, and efficacy-related clinical laboratory tests (serum levels of troponin T, troponin I, and NT-pro-BNP) will be determined every 6 months. In addition, echocardiograms will be performed every 12 months on an annual basis.

An end of study visit including all safety and efficacy assessments will occur upon subject completion of the study, premature withdrawal (for any reason), or in the event of program discontinuation by the Sponsor.

Statistical Methods:

Safety and efficacy data will be summarized using descriptive statistics. For continuous variables, the means, standard deviations, medians, and ranges will be presented; for categorical variables, counts and percentages (with 95% confidence intervals) will be presented. Safety and efficacy data will also be shown in individual subject listings.

The cumulative efficacy data (starting from Protocol Fx1B-201) as measured by the Patient Global Assessment, NYHA classification, KCCQ, 6-minute walk test, echocardiograms, and serum levels of troponin I, troponin T, and NT-pro-BNP will be presented.

The endpoints of mortality and hospitalization (all cause and cardiac-related) will be analyzed individually and as composite measures. A Kaplan-Meier plot of time to event from the baseline of Protocol Fx1B-201 will be generated, and the event rate and associated 95% confidence intervals will be presented at 1, 2, 3, and 4 year intervals since the start of the investigational drug. The baseline data from protocol Fx1B-201 will be used as baseline for the analyses. Interim analyses will be performed during the course of the study to allow for the reporting of safety and efficacy data from the ongoing study.

SCHEDULE OF ACTIVITIES

The Schedule of Activities table provides an overview of the protocol visits and procedures. Refer to Study Procedures (Section 6) and Assessments (Section 7) for detailed information on each procedure and assessment required for compliance with the protocol.

Procedure/Evaluation	End of study visit from Fx1B-201 and/or Day 0 (baseline)	Open-label Investigational Product			End of Study Visit ^a
		Day 1	Telephone (every 3 months between clinic visits)	Clinic Visit (every 6 months)	
		±1 week	±1 week	±2 week	±2 week
Informed consent	X				
Inclusion/exclusion criteria	X				
Demographics	X				
Medical history	X				
Complete physical examination					X
Abbreviated physical examination	X ^b			X	
Blood/urine sample for laboratory testing ^g	X ^b			X	X
Enrollment	X				
First dose of tafamidis		X ^d			
Patient Global Assessment				X	X
NYHA Classification				X	X
KCCQ				X	X
6-Minute walk test				X	X
Echocardiogram				Annually ^e	X ^f
Electrocardiogram				Annually ^e	X ^f
Adverse events	X		X	X	X
Concomitant medication	X		X	X	X
Tafamidis compliance and accountability				X	
Dispense tafamidis ^c	X		X	X	

^a An end of study visit will occur upon subject completion of study, subject withdrawal (for any reason), or study discontinuation by the Sponsor.

^b The physical examination (including weight and vital signs) results from the end of study visit from Protocol Fx1B-201 will be used for Day 0 of Protocol Fx1B-303. If more than 30 days has elapsed, then a brief physical examination must be performed on Day 0.

^c Subjects will be given a 3-month supply of investigational product on Day 0. Subjects will return to the clinical unit every 6 months and will receive a 3-month supply of investigational product. At 3-month intervals between clinic visits, 3-month supplies of investigational product will be mailed directly to subjects from the clinical site.

^d Subjects will self-administer study medication at home beginning on Day 1.

^e Echocardiograms and ECGs will be performed on an annual basis (every 12 months).

^f Echocardiograms and ECGs will be performed only if the previous assessments occurred more than six months prior to the end of study visit.

^g Laboratory tests listed in Section 7.3.

^h Clinical laboratory test results from the end of study visit from Protocol Fx1B-201 will be used for Day 0 of Protocol Fx1B-303. If more than 30 days has elapsed, then clinical laboratory tests must be performed on Day 0.

TABLE OF CONTENTS

LIST OF TABLES	13

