6.1. Screening/Baseline Assessment

The end of study physical examination (including weight and vital signs) and the relevant clinical laboratory assessments from Protocol Fx1B-201 will be used as the Day 0 assessments for Protocol Fx1B-303. If more than 30 days has elapsed between the final study visit of Protocol Fx1B-201 and Day 0 of Fx1B-303, an abbreviated physical examination (including weight and vital signs) and clinical laboratory assessments must be performed on Day 0.

Subjects will be required to sign an informed consent form before beginning participation in Protocol Fx1B-303. The following procedures will be performed on Day 0:

- All inclusion and exclusion criteria will be reviewed to ensure eligibility for participation in this study.
- Demographics (date of birth, age, gender, and race) for all subjects will be collected.
- A complete medical history will be obtained.
- Abbreviated physical exam including weight and vital signs (if not conducted within 30 days of Day 0).
- Collect blood/urine samples for clinical laboratory assessments (Section 7.3) (if not collected within 30 days of Day 0).
- Ask subjects non-leading questions such as “How do you feel?” and record adverse events.
- Record concomitant medications.
- Dispense 3 month supply of investigational product with instructions that subject is to administer the first dose at home on the following day as instructed (Section 5.2.3).

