9.2. Efficacy Analysis

9.2.1. Analysis of Primary Endpoint

For subjects who enroll into this protocol, the cumulative efficacy data (starting from Protocol Fx1B-201) as measured by the Patient Global Assessment, NYHA classification, KCCQ, 6-minute walk test, echocardiograms, and serum levels of troponin I, troponin T, and NT-proBNP will be presented.

Baseline data from protocol Fx1B-201 will be used as baseline for these analyses.

Subjects who enroll into the study and receive any amount of investigational product will be included in the safety population. Subjects who receive any amount of investigational product and have at least one post-baseline efficacy assessment will be included in the efficacy population.

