## 8. STATISTICAL METHODOLOGY AND STATISTICAL ANALYSES

### 8.1. Statistical Methods

#### 8.1.1. Analyses for Continuous Data

All continuous data will be summarized with descriptive statistics, including mean, standard deviation, median, IQR, range and 95% confidence intervals. In addition, change from baseline statistics will be presented as appropriate, to include the appropriate descriptive statistics. For analysis of change from baseline, baseline data from protocol Fx1B-201 will be used as baseline for these analyses. For the change from baseline statistics, the estimate will be adjusted for baseline and the LSMean and standard error will be presented with the 95% confidence interval based on an MMRM model with a random effect for subject and covariate of baseline.

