### **Appendix 2. Definition and Use of Visit Windows in Reporting**

For the purpose of this study, Day 1 is defined as the first dose day under this protocol.

Day 1  $\pm$  1 week

Every other 3 month telephone visits between clinic visits  $\pm$  1 week

Clinic visits every 6 months  $\pm$  2 weeks

End of study visit  $\pm$  2 weeks

However, in order to maximize the use of all available data, the visit windows for each visit are expanded as follows:

Day 0: End of study visit from Fx1B-201

Day 1 + 1.5 months

Telephone contact (every 3 months between clinic visits)  $\pm$  1.5 months

Clinic visits (every 6 months)  $\pm$  3 months

End of study visit (see details below)

In the event that there is a break between the last visit of the parent study (Fx1B-201,) and the first day of dosing in the current study Fx1B-303 (B3461026); then the visit associated with the first day of enrollment in the current study Fx1B-303 (B3461026) will be the baseline visit of this study.

For an early termination visit within study B3461026 (Fx1B-303): The existing windowing rules will be used and as such, the data in the early termination visit should never replace an existing visit. If the visit covered by the windowing rules above is already populated with an existing visit, then the EOS visit should be mapped forward to the next clinic visit.

As an example, the EOS visit occurs at month 68.

If there is no month 66 visit, then the EOS visit becomes the month 66 visit.

If there is a month 66 visit, then the EOS visit becomes the month 78 visit.

For an unscheduled visit:

If possible, the existing windowing rules will be used, but the data should never replace an existing visit. If the visit is already populated, then the unscheduled visit should be mapped forward to the next appropriate visit for that measure if that visit is available.

As an example, the unscheduled visit occurs at month 68 and the data are collected annually.

If there is no month 66 visit, then the unscheduled visit becomes the month 66 visit.

If there is a month 66 visit, but no month 78 visit then the unscheduled visit becomes the month 78 visit.

If there are both month 66 and month 78 visits, then the unscheduled visit is not included in the summary analyses but is included in the listing as unscheduled.

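### Cumulative efficacy change is taken from the Fx1B-201 baseline but Fx1B-303 visits are counted from the first Fx1B-303 dose, so any break between the studies drops out of the efficacy time axis

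*Protocol*

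**What the plan says.** **Scope.** Protocol Summary, Statistical Methods, announces the presentation of "The cumulative efficacy data (starting from Protocol Fx1B-201) as measured by the Patient Global Assessment" and the other efficacy measures.

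**Baseline for change.** Protocol 9.2.1: "Baseline data from protocol Fx1B-201 will be used as baseline for these analyses". SAP 8.1.1 agrees for continuous data: "baseline data from protocol Fx1B-201 will be used as baseline for these analyses".

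**Visit clock.** SAP Appendix 2: "For the purpose of this study, Day 1 is defined as the first dose day under this protocol". The expanded analysis windows, plus or minus 3 months for clinic visits, follow from that day. The same list has "Day 0: End of study visit from Fx1B-201".

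**Time-to-event clock.** SAP 8.1.3 gives yearly Kaplan-Meier estimates from the start of drug in Fx1B-201.

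**Breaks.** Protocol 4.1 and 4.2 require completion of Fx1B-201 and set no maximum interval before entry. Protocol 6.1 covers longer intervals: "If more than 30 days has elapsed between the final study visit of Protocol Fx1B-201 and Day 0 of Fx1B-303, an abbreviated physical examination" and laboratory tests are done on Day 0. The Schedule of Activities has no Day 0 entry for the Patient Global Assessment (PGA), NYHA class, KCCQ, 6-minute walk or echocardiogram.

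**Fx1B-303 baseline.** SAP 6.7 uses the measurement from the Fx1B-201 final visit or Day 0, whichever is later. Appendix 2 says that after a break "the visit associated with the first day of enrollment in the current study Fx1B-303 (B3461026) will be the baseline visit of this study".

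**The concern.** The cumulative analysis joins two studies into one course from one baseline, but nothing in the SAP carries the interval between them onto that course. Subjects who rolled over directly and subjects who entered after a break share a visit cell and a model time point, although they are at different distances from the baseline that their change is measured against. The survival curve from the same start does count the interval, so the two displays do not line up.

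Long-term efficacy data are a stated objective, and SAP 3.2 foresees interim reporting at meetings, in publications and for regulatory purposes. With up to 35 subjects expected, a few long breaks could move a visit mean.

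**Working it through.** The plan states no figure to reproduce. The check sets the rules side by side and then illustrates scale.

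**Inputs**
- Fx1B-201 lasted 12 months (Protocol 1.2.2).
- m is months since the first Fx1B-303 dose (SAP Appendix 2).
- g is the break in months. The documents do not give it.
- Mean 6-minute walk change over 12 months was -11 m on tafamidis in Fx1B-201 and -44 m in the natural-history cohort, TRACS (Protocol 1.2.4).

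**Step 1: elapsed time.** Time from the Fx1B-201 baseline is about 12 + g + m. Without a break it is 12 + m. The discrepancy is g at every later visit. At Fx1B-303 Month 6, subjects with g = 0, 3 and 6 stand at 18, 21 and 24 months. All three values enter the Month 6 summary as change from the same baseline. The Kaplan-Meier clock places the same subjects at 18, 21 and 24 months.

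**Step 2: what is measured around a break.**
- NYHA, KCCQ and 6-minute walk are next measured at Month 6, and the echocardiogram at Month 12. Change in the break is merged with change in the following interval.
- Troponin I, troponin T and NT-proBNP are repeated on Day 0 after more than 30 days. Their change over such a break is visible, although their later visits have the same clock discrepancy.
- The follow-up PGA question (Protocol Appendix 1) refers to the last study visit. Its first Fx1B-303 answer may span the break, but it is not a change from a fixed baseline.

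**Step 3: the Fx1B-303 baseline.** Take a walk test after a break. SAP 6.7, read per measurement, returns the Fx1B-201 final value because no Day 0 walk exists. Appendix 2 points to the enrolment visit, where none is scheduled, so its rule returns no value. Appendix 2 also applies to any break, whereas the Protocol repeats tests only after more than 30 days.

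**Step 4: scale, as an illustration.** Assume linear change.
- On-drug rate: -11/12 = -0.92 m per month.
- Natural-history rate: -44/12 = -3.67 m per month.
- Expected change at Fx1B-303 Month 6 without a break: 18 x (-11/12) = -16.5 m.

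| Break | Added, on-drug rate | Added, natural-history rate | Month 6 total, on-drug | Month 6 total, natural-history |
|---|---|---|---|---|
| 30 days (0.99 months) | -0.9 m | -3.6 m | -17.4 m | -20.1 m |
| 3 months | -2.75 m | -11 m | -19.25 m | -27.5 m |
| 6 months | -5.5 m | -22 m | -22.0 m | -38.5 m |
| 12 months | -11 m | -44 m | -27.5 m | -60.5 m |

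These are per affected subject. The shift in a visit mean is the share affected times the added amount. If one third had a 3-month break (an assumed share), it would be -2.75/3 = -0.9 m to -11/3 = -3.7 m.

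**The case against.** The strongest reply is that direct rollover is the default. The Schedule of Activities merges the Fx1B-201 final visit with Day 0, and the 30-day rule is a contingency. No document shows that any long break occurred. The study is descriptive, without hypotheses, and a shift of a few metres is small beside the 75 m width of the middle walk categories (300 to 375 m, 375 to 450 m). Individual listings are planned. All of this limits the size of the point. None of it supplies a rule for elapsed time when a break does occur, and the SAP itself provides for one.

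Three stronger readings are tempting and not supported.

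- **Breaks were off drug, so untreated decline is reported as decline on tafamidis.** Dosing during a break is not stated. The Protocol Summary has subjects begin dosing on Day 1; SAP Section 2 has them continue, and Protocol 1.2.2 also speaks of continuing. These passages must be reconciled. If drug was taken throughout, the attribution is right and only the timing is wrong.
- **A break over 3 months puts every later value in the wrong window.** Appendix 2 windows are defined on the Fx1B-303 clock, and an on-time Month 6 visit is inside its window whatever the break. A month-18 window of 15 to 21 months appears nowhere. The 12 + m position is an inference from treating Day 0 as the Fx1B-201 final visit; the SAP does not say how the cumulative axis is labelled.
- **The baseline conflict biases change from baseline.** It does not. Change uses the Fx1B-201 baseline; SAP 6.7 says only that the Fx1B-303 baseline will be summarised.

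**Conclusion.** The point holds as a gap in the SAP. Under the stated rules, any break places later cumulative efficacy values g months too early relative to subjects without one, out of step with the survival analysis. For NYHA, KCCQ, 6-minute walk and echocardiogram, change during the break cannot be isolated. The Appendix 2 break rule and SAP 6.7 give different Fx1B-303 baselines for those endpoints, and this needs correcting whatever the break lengths.

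The actual size is unknown. The illustrative range for a 3-month break, -2.75 to -11 m of walk distance per affected subject, rests on linear change, on rates from two small uncontrolled cohorts (35 and 29 patients), and on an assumed break. It shows scale and is not an estimate of bias in this trial. The correction is worth making because it is cheap and would show at once whether breaks matter.

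**What to change.** In SAP Appendix 2 and 8.1.1:

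1. Base the time axis of the cumulative change-from-baseline tables and the MMRM on days since the first tafamidis dose in Fx1B-201, the clock of 8.1.3. Keep the Fx1B-303 windows for study-specific summaries.
2. List each subject's break between the Fx1B-201 final visit and the first Fx1B-303 dose.
3. Repeat the cumulative summaries without subjects whose break exceeds 30 days, the threshold already in Protocol 6.1.
4. Define the Fx1B-303 baseline per endpoint as the last value before the first Fx1B-303 dose, in place of the Appendix 2 break sentence.
5. Reconcile the Protocol and SAP wording on dosing at entry.

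The cost is SAP text, reprogrammed visit assignment from dates already held, and one extra set of summaries. No new assessment is needed, but none of this recovers functional change in a break that was not measured. Some visits will move, mainly annual echocardiograms. With a 3.5-month break, the first falls at 12 + 3.5 + 12 = 27.5 months, outside a 21 to 27 month window around month 24. The SAP should say in advance how such values are tabulated.

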1.2.2. Study Rationale

The initial development activities for tafamidis were undertaken in patients with TTR-FAP. Safety data in this population, and the results from the TRACS study, led to the initiation of Protocol Fx1B-201, a 12-month trial of tafamidis in patients with TTR-CM. The results of the Fx1B-201 study will be used in the design of a Phase 3 program that will evaluate the efficacy and safety of tafamidis in TTR-CM.

TTR-CM is a slowly progressing disease with a median survival of approximately 60 months [14, 15]. It is currently not known whether tafamidis will be effective in slowing or halting the progression of TTR amyloid cardiomyopathy, or when such an impact would become evident. Therefore, the purpose of the current study is to assess the long-term safety and

efficacy of tafamidis in patients with ATTR-CM. Eligible patients who successfully completed Protocol Fx1B-201, having received open-label tafamidis for 12 months, may enroll in Protocol Fx1B-303 and continue to receive open-label tafamidis for up to an additional 10 years.

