7.5. Adverse Events

Starting from the date the informed consent form is signed, adverse events (AEs) will be recorded in the CRF and monitored throughout the study. All adverse events should be monitored until they are resolved or are clearly determined to be due to a subject's stable or chronic condition or intercurrent illness(es). All AEs will be recorded on the CRF. Definitions, documentation, and reporting of AEs are described in Section [9](#).

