8.2. Reporting Period

For SAEs, the active reporting period to Pfizer or its designated representative begins from the time that the subject provides informed consent, which is obtained prior to the subject's participation in the study, ie, prior to undergoing any study-related procedure and/or receiving investigational product, through and including 28 calendar days after the last administration of the investigational product. Should an investigator be made aware of any SAE occurring any time after the active reporting period, it must be promptly reported.

- AEs (serious and non-serious) should be recorded on the CRF from the time the subject has taken at least one dose of study treatment through last subject visit.

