9.2.8. Mortality and Hospitalization

The endpoints of mortality and hospitalization (all cause and cardiac-related) will be analyzed individually and as composite measures.

A Kaplan-Meier plot of time to event from the start of Protocol Fx1B-201 will be generated, and the event rate and associated 95% confidence intervals will be presented at 1, 2, 3, and 4 years since the start of the investigational drug.

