**8. Mortality and hospitalization (all-cause and cardiac-related)**

All-cause of mortality is defined as any death occurring during the study. Cardiac-related mortality will be any mortality meeting the following MedDRA criterion: 1) AE body system (AEBODSYS) = "CARDIAC DISORDERS", or 2) AE preferred term (AEDECOD) in (CHEST DISCOMFORT, CHEST PAIN, DEATH, CEREBROVASCULAR ACCIDENT, EMBOLIC STROKE, DISEASE

PROGRESSION). Description on the time to mortality analysis can be found in [Section 8.1.3](#).

All cause of hospitalization is defined as any adverse event for which SAE type “3=Hospitalization” in the Adverse Event (AE) CRF. The cardiac-related hospitalization will be any hospitalization meeting the following MedDRA criterion:1) AE body system (AEBODSYS) = “CARDIAC DISORDERS”, or 2) AE preferred term (AEDECOD ) in (CHEST DISCOMFORT, CHEST PAIN, DEATH, CEREBROVASCULAR ACCIDENT, EMBOLIC STROKE, DISEASE PROGRESSION).

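### If time to hospitalization is analysed from the start of Fx1B-201, no stated rule counts an admission in a break between the two studies, yet that time stays in the risk set as event-free

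*Protocol*

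**What the plan says.** **Time origin.** The Protocol Summary (Statistical Methods) and Protocol 9.2.8 analyse mortality and hospitalization individually and as composites. The Summary states "A Kaplan-Meier plot of time to event from the baseline of Protocol Fx1B-201 will be generated", and Section 9.2.8 states "A Kaplan-Meier plot of time to event from the start of Protocol Fx1B-201 will be generated". In the Summary, rates are "presented at 1, 2, 3, and 4 year intervals since the start of the investigational drug". SAP 8.1.3 likewise applies Kaplan-Meier to time-to-event endpoints, with yearly intervals from the Fx1B-201 baseline.

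**Break between studies.** Fx1B-201 was "a 12-month trial of tafamidis in patients with TTR-CM". The Protocol Summary (Study Design) covers the case "If more than 30 days has elapsed between the final study visit of Protocol Fx1B-201 and Day 0 of Protocol Fx1B-303", and Protocol 6.1 does the same. The only consequence is a repeat examination and laboratory tests. SAP Appendix 2 also allows for a break and redefines only the baseline visit. No maximum is stated.

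**Start of event recording.** Protocol 7.5: "Starting from the date the informed consent form is signed, adverse events (AEs) will be recorded in the CRF". Protocol 8.2: "AEs (serious and non-serious) should be recorded on the CRF from the time the subject has taken at least one dose of study treatment". The two rules differ, and neither reaches back before consent.

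**Source of events.** SAP 6.2 item 8: "All cause of hospitalization is defined as any adverse event for which SAE type" 3 is marked on the adverse-event CRF.

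**Risk set.** SAP 7 censors at the last observation. SAP 8.1.3 uses delayed entry only for death from symptom onset. No rule covers time between the studies.

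**Hospitalization in the SAP.** SAP 8.3 gives time origins and censoring rules for mortality only, and reports hospitalization as number and percentage.

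**The concern.** Kaplan-Meier treats a subject in the risk set as someone whose event would be seen if it happened. During a break that condition is not secured by any stated rule: an admission may surface in the Day 0 medical history, but nothing turns it into an endpoint event. The subject is then carried forward as event-free.

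The resulting error goes one way, towards a lower hospitalization or composite rate at years 2 to 4. The study has no control group, and Protocol 1.2.4 already sets the 12-month Fx1B-201 hospitalization rate beside the TRACS natural-history cohort. A longer-term rate that is low for a procedural reason would invite the same comparison.

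The mechanism concerns hospitalization, alone or within the composites. A subject has to be alive at Day 0 to enrol, so the break hides no deaths among enrolled subjects.

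**Working it through.** **Inputs (Protocol 1.2.4).** In Fx1B-201 over 12 months: cardiovascular hospitalization 9/35 = 25.7%, death 2/35 = 5.7%, composite 9/35 = 25.7%. In TRACS: cardiovascular hospitalization 10/29 = 34.5%. All four percentages reproduce as stated.

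**Subjects at risk.** Hospitalization and the composite both count 9, so both deaths were among hospitalized subjects. At most 35 − 2 = 33 can enter Fx1B-303. Of these, 9 − 2 = 7 already have the event and 26 are event-free.

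**Assumptions.** Constant hazard; the break starts at month 12; every subject has the same break of g days; no event in the break is recorded; hospitalization recurs at the same hazard afterwards. The break length and the share of subjects with a break are not in the documents.

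**Hazard.** λ = −ln(1 − 9/35) = 0.297 per year.

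**Unseen first events.** 26 × [1 − exp(−λg/365.25)].

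**Two-year rate.** Full capture: 1 − (26/33) × exp(−0.297) = 41.5%. Break counted as event-free: 1 − (26/33) × exp[−0.297 × (1 − g/365.25)].

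| Break, all subjects | Unseen first events | 2-year rate reads | Shortfall (points) |
|---|---|---|---|
| none | 0 | 41.5% | 0 |
| 30 days | 0.6 | 40.0% | 1.4 |
| 60 days | 1.2 | 38.5% | 2.9 |
| 90 days | 1.8 | 37.0% | 4.4 |

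For scale, a full year at this hazard gives 26 × 9/35 = 6.7 first events among the 26.

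**Other assumptions.** With one constant hazard from month 0 instead of the 33-subject base, the 2-year rate of 44.8% reads 43.4%, 40.6%, 36.0% or 25.7% for breaks of 1, 3, 6 or 12 months. At the TRACS hazard, 57.1% reads 55.5% (1 month) or 52.3% (3 months). The gap narrows with time: at the Fx1B-201 hazard with a 3-month break, the 4-year rate of 69.5% reads 67.2%. Year 1 stays at 25.7% throughout.

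**Does removing the break from the risk set help?** A simulation of 40,000 subjects at the Fx1B-201 hazard with a 6-month break gave these 2-year rates:

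| Share with break | Truth | Break kept as event-free | Break removed (start-stop) |
|---|---|---|---|
| half | 45.1% | 40.6% | 44.9% |
| all | 44.7% | 35.9% | 35.9% |

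When everyone shares the same break, nobody is at risk during it, so the curve stays flat and nothing is corrected. Retrieving the events is the only remedy in that case.

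**The case against.** The strongest objection is that the SAP does not specify the analysis in question. SAP 8.3 reports hospitalization as number and percentage, Protocol 9 lets the SAP modify the protocol's plans, and SAP 8.1.3 never names hospitalization. This stands as a limit: the point applies only if the protocol's Kaplan-Meier or composite analysis is run. That analysis remains in current protocol text, so the two documents have to be reconciled either way.

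A reader might infer four stronger things that the documents do not support.

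- *That no admission in the break was recorded.* The Fx1B-201 rules on events after its final visit are not available here, and Day 0 includes a complete medical history. What can be said is that no stated rule makes such an admission an endpoint event.
- *That long breaks are expected or unlimited.* The wording is conditional and states no maximum. The Schedule of Activities combines the Fx1B-201 end-of-study visit and Day 0 in one column, so direct rollover is provided for.
- *That subjects were off drug in the break.* Nothing says so, and SAP 2 describes dosing as continuing.
- *That all reported rates are too low.* Year 1 is unaffected if the break starts after month 12, and a direct rollover adds no bias.

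The size is also modest against sampling error: a simple binomial 95% interval around 41.5% with 33 subjects is about ±17 points. No hypothesis is tested. Even so, a wide interval does not excuse a one-directional error that is cheap to remove.

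**Conclusion.** The point holds conditionally. Followed as written, the protocol's time-to-hospitalization and composite analyses count any break as event-free follow-up without a rule for capturing admissions in it. The bias is downward at years 2 to 4 for subjects with a break, provided the analysis is run and Fx1B-201 did not itself collect events after its final visit.

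For breaks of 30, 60 or 90 days, the 2-year shortfalls of 1.4, 2.9 and 4.4 points are upper values at the Fx1B-201 hazard because they give every subject the break; they shrink roughly with the share who had one. Longer breaks would do more. The sizing is for cardiovascular hospitalization; the documents give no all-cause rate from which to size that endpoint.

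**What to change.** 1. For each enrolled subject, retrieve the date and reason of every hospital admission between the final Fx1B-201 visit and the start of Fx1B-303 adverse-event recording, from the Day 0 history or site records. Count these as events in Protocol 9.2.8 and SAP 6.2 item 8.
2. Report the distribution of break lengths, including how many subjects rolled over directly. If Fx1B-201 did collect events after its final visit, say so and for how long.
3. Only where retrieval fails, use start-stop risk sets with more than one record per subject, excluding the break. State that this does not correct the rate if all subjects share the same break. The SAP Appendix 4 code would need restructuring: it handles death from symptom onset with a single entry time per subject, not an internal gap.
4. Reconcile Protocol 9.2.8 with SAP 8.3 on whether hospitalization and the composites are time-to-event endpoints.
5. Reconcile Protocol 7.5 with 8.2 on when adverse-event recording starts.

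The cost is a few lines of text, a look-back for at most 33 subjects, and possibly a slightly less favourable reported event rate.
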